### **7.2.2. MTD Definition**

The MTD would be any doses with true toxicity probabilities in the Equivalence Interval (EI) where the EI is defined as [20%-30%].

In practice, the MTD will be the highest dose associated with the occurrence of DLTs  $\leq 33\%$  (eg, 3/9 evaluable patients experience a DLT during the first treatment cycle).

### **7.2.3. Recommended Phase 2 Dose (RP2D) Definition**

The Recommended Phase 2 Dose (RP2D) is the dose chosen for further study based on Part 1 results. If the MTD proves to be clinically feasible for long term administration in a reasonable number of patients, such dose usually becomes the RP2D. Further experience with the MTD may result in a RP2D dose lower than the MTD.

### **7.2.4. Vitals Signs**

Vital signs, See Schedule of Activities in the protocol for details.

### **7.2.5. Laboratory Data**

The laboratory results will be graded according to the NCI CTCAE v4.03 severity grade. For labs for which an NCI CTCAE v4.03 scale does not exist, the frequency of subjects with values below, within, and above the normal ranges will be summarized by dose. Baseline evaluations for laboratory data are those collected:

- Within 28 days prior to Cycle 1/Day 1.
- Closest but prior to Cycle 1/Day 1 if there is more than one baseline evaluation.

### **7.2.6. Adverse Events**

Assessment of adverse events will include the type, incidence, severity (graded by the National Cancer Institute Common Terminology Criteria for Adverse Events [NCI CTCAE] version 4.0) timing, seriousness, and relatedness.

All AEs will be coded by system organ class (SOC) and preferred term using Medical Dictionary for Regulatory Activities (MedDRA). The severity of all AEs will be graded by the investigator using NCI CTCAE Version 4.03 whenever possible. For other AEs without specific CTC definitions, results are identified according to CTCAE “other” categories. Adverse events will be assigned to the appropriate cycle based on Day 1 of each cycle.

#### **Treatment Emergent Adverse Events**

- All deaths from start of treatment until 28 days after the final dose.
- All treatment related SAEs.
- All unrelated SAEs from treatment start until 28 days after final dose of treatment.

- All non-fatal AEs occurring after treatment start up until 28 days after final dose of treatment or until start of new anti-cancer treatment, whichever is first.
- Disease progression is not considered a treatment emergent adverse event unless the subject dies of disease prior to 28 days after discontinuation of treatment.
- Events that are continuations of baseline abnormalities are considered treatment emergent adverse events only if there is an increase in grade over baseline.

### **Treatment Related Adverse Events**

Treatment Related Adverse Events are treatment emergent adverse events with cause categorized by the investigator as related to study treatment. Events that are continuations of baseline abnormalities (signs and symptoms) are not considered treatment emergent, and hence are not considered treatment related, unless there is an increase in grade over baseline.

#### **7.2.7. ECG and QTc Interval**

The analysis of ECG results will be based on Safety Population patients with baseline and on-treatment ECG data.

ECG measurements will be used for the statistical analysis and all data presentations. Any data obtained from ECGs repeated for safety reasons after the nominal time-points will not be averaged along with the preceding values. Interval measurements from repeated ECGs will be included in the outlier analysis as individual values obtained at unscheduled time points.

QT intervals will be corrected for heart rate (QTc) using standard correction factors (ie, Bazett's, Fridericia's and possibly a study specific factor). The adequacy of the correction method will be assessed graphically (plots of QT and QTc versus RR) and supplementary transformations may be considered, as appropriate. Data will be summarized and listed for QT, HR, RR, PR, QRS, QTcF and QTcB by treatment and dose. Individual QTc (all evaluated corrections) intervals will be listed by compound, time and dose. The most appropriate correction factor will be selected and used for the following analyses of central tendency and outliers and used for the study conclusions. Descriptive statistics (n, mean, median, standard deviation, minimum, and maximum) will be used to summarize the absolute QTc value and changes from baseline in QTc after treatment by compound, dose and by time point. For each patient and by treatment, the maximum change from baseline will be calculated as well as the maximum post-baseline value across time-points. Outlier analysis of the QTc data will be conducted and summarized as follows:

- The number of patients with maximum change from baseline in QTc (<30, 30-60, and  $\geq 60$  ms).
- The number of patients with maximum post-dose (post-baseline) QTc (<450, 450-<480, 480-<500, and  $\geq 500$  ms).

In addition, the number of patients with corrected and uncorrected QT values  $\geq 500$  msec will be summarized.

Shift tables will be provided for baseline vs. worst on study QTc (one or more correction method will be used) using Maximum CTC AE Grade. As well as tables of ECG abnormality at baseline (yes, no, not done: (n, %)). Patients experiencing clinically-relevant morphological ECG changes will be summarized (including frequency and percentage).

If more than one ECG is collected at a nominal time post dose (for example, triplicate ECGs), the mean of the replicate measurements will be used to represent a single observation at that time point. If any of the three individual ECG tracings has a QTc value  $\geq 500$  msec, but the mean of the triplicates is not  $\geq 500$  msec, the data from the subject's individual tracing will be described in a safety section of the study report in order to place the  $\geq 500$  msec value in appropriate clinical context. However, values from individual tracings within triplicate measurements that are  $\geq 500$  msec will not be included in the categorical analysis unless the average from those triplicate measurements is also  $\geq 500$  msec. Changes from baseline will be defined as the change between QTc post dose from Day 0, or the pre-dose values on Day 1.

The effect of drug concentrations on QTc change from baseline will be explored graphically. Additional concentration-QTc analyses may be performed. Data may be pooled with other study results and/or explored further with PK/PD models.

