## **6.3. Safety Analysis Set**

The safety analysis set includes all enrolled patients who receive at least one dose of study medication.

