#### **QTc**

For the QTc analyses, no values will be imputed for missing data.

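### The ECG population rule requires a baseline tracing even for absolute QT/QTc outlier counts that use only post-dose values, and it conflicts with the planned not-done row for baseline ECG

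*SAP*

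**What the plan says.** Section 7.2.7 of the SAP opens with a single population statement for ECG data: "The analysis of ECG results will be based on Safety Population patients with baseline and on-treatment ECG data". Two conditions are therefore added to the Safety Analysis Set, which Section 6.3 defines without any ECG requirement: "The safety analysis set includes all enrolled patients who receive at least one dose of study medication".

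The same section then plans several outputs:

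- A change output: "The number of patients with maximum change from baseline in QTc", in three bands.
- An absolute output: "The number of patients with maximum post-dose (post-baseline) QTc", in four bands, the highest being 500 ms or more.
- A second absolute output: "In addition, the number of patients with corrected and uncorrected QT values" of 500 msec or more.
- Shift tables of baseline against worst on-study QTc grade.
- A baseline description: "tables of ECG abnormality at baseline (yes, no, not done: (n", with percentages.

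The QTc paragraph of Section 8.3 adds: "For the QTc analyses, no values will be imputed for missing data".

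Nothing in Section 7.2.7 says that the absolute outputs use a different population from the change outputs.

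**The concern.** A maximum post-dose QTc, or a count of patients reaching 500 msec, is computed from on-treatment tracings alone. Requiring a baseline tracing removes patients whose data are sufficient for the output. The patient who matters is one who was dosed, has no baseline ECG and reaches 500 msec or more on treatment. That patient belongs to the Safety Analysis Set but, on the literal rule, appears in neither the numerator nor the denominator of the two absolute counts.

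The adverse event and laboratory summaries in Section 9.2.3 use the Safety Analysis Set with no such condition. The SAP also gives the 500 msec threshold special attention elsewhere: Section 7.2.7 asks for a written description when one tracing of a triplicate reaches it but the mean does not. No comparable provision covers a patient left out for lack of a baseline. In small cohorts, one omitted patient can be the difference between no case reported and one case reported.

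**Working it through.** The SAP states no figure on this point, so there is none to reproduce. The check applies the population sentence to each planned output and then illustrates the size.

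**Step 1. Which outputs need a baseline?** Take a dosed patient with on-treatment ECGs and no baseline ECG.

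| Output in Section 7.2.7 | Baseline needed to compute it? | This patient under the literal rule |
|---|---|---|
| Maximum change in QTc | Yes | Excluded, necessarily |
| QTc shift table | Yes, unless a missing-baseline row is added | Excluded |
| Maximum post-dose QTc bands | No | Excluded, though computable |
| QT or QTc of 500 msec or more | No | Excluded, though computable |
| Baseline ECG abnormality, with a not-done category | The category exists for patients without one | Excluded, leaving the category empty |

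The third and fourth rows show the rule reaching further than the arithmetic requires. The last row shows the section disagreeing with itself: if the population sentence binds every table, nobody without a baseline ECG can be entered as not done.

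**Step 2. Direction of the effect.** Let x of n patients with on-treatment ECGs have the event. Suppose m of the n lack a baseline, and e of those m have the event. The reported result changes from x/n to (x − e)/(n − m).

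- Count: x − e is never more than x, so the count can only stay the same or fall.
- Percentage: it falls when e/m exceeds x/n and rises when e/m is below x/n. For example, with one event among 15 patients and one event-free patient lacking a baseline, 1/15 = 6.7% becomes 1/14 = 7.1%.

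**Step 3. Illustration of size.** The SAP does not say how many patients will lack a baseline ECG. If none do, nothing changes. The table assumes exactly one (m = 1), who has a value of 500 msec or more (e = 1), with no other event (x = 1). The sizes are the minimum of 9 at the MTD (Section 2.2), about 15 per tumor type and about 30 in Part 2 (Section 2.1). The intervals are exact (Clopper-Pearson), since Section 9.1 specifies an exact method for binary endpoints. For x events in n patients, the lower limit is the 0.025 quantile of Beta(x, n − x + 1), or 0 when x = 0. The upper limit is the 0.975 quantile of Beta(x + 1, n − x).

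| Group | All with an on-treatment ECG | Rule as written |
|---|---|---|
| 9 at the MTD | 1/9 = 11.1% (0.3% to 48.3%) | 0/8 = 0% (0% to 36.9%) |
| One tumor type | 1/15 = 6.7% (0.2% to 32.0%) | 0/14 = 0% (0% to 23.2%) |
| Part 2 overall | 1/30 = 3.3% (0.1% to 17.2%) | 0/29 = 0% (0% to 11.9%) |

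The intervals overlap widely. What changes is whether a case is counted, not the precision of the estimate.

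**The case against.** The other side has a fair case.

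- **Scope.** The not-done category suggests that the opening sentence was never meant to bind every table. This stands, and it makes the defect partly one of unclear scope. It does not settle the absolute counts, because no exception is written for them and a programmer following the text would exclude the patient.
- **Other routes to the value.** Section 7.2.7 plans listings of individual QTc values, Appendix 1 asks for qualifying measurements to be listed, and a QTc prolongation reported as an adverse event would be summarized on the Safety Analysis Set. This limits the harm. However, the SAP names no separate population for the listings, the adverse event route depends on investigator reporting, and neither restores the summary count.
- **Interpretation.** Without a baseline, a high QTc cannot be distinguished from a pre-existing abnormality, and one population gives one denominator throughout. This is a good reason to keep the condition for change and shift outputs. A threshold count is defined without reference to baseline.
- **Consequence.** The study is descriptive (Sections 4.1 and 9.1), and none of the dose-escalation, DLT or MTD rules refers to this count. This stands.

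Three stronger readings are tempting, and the SAP does not support them. A reader might take the not-done category as proof that patients without a baseline ECG exist or are expected; it shows only that the table allows for them. A reader might infer that the exclusion always understates risk; that is true of the count but not of the percentage. A reader might treat the no-imputation rule in Section 8.3 as the cause; it only leaves a missing baseline missing and has no bearing on whether an observed post-dose value is counted.

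**Conclusion.** The point holds as a minor defect of scope. As written, Section 7.2.7 applies a baseline requirement to two absolute QT/QTc outputs that do not need one, and it contradicts its own not-done category. A treated patient with no baseline ECG and a value of 500 msec or more would be left out of those counts.

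The practical effect is probably small. It needs a dosed patient without a baseline ECG, and that patient must also reach the threshold. The SAP gives no frequency for either, and the protocol's ECG schedule was not available. The figures of 1/9 against 0/8, 1/15 against 0/14 and 1/30 against 0/29 rest entirely on the assumption of one such patient and no other event. They are not forecasts. The conclusion also takes the Safety Population named in Section 7.2.7 to be the Safety Analysis Set of Section 6.3.

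**What to change.** Replace the opening population sentence of Section 7.2.7 with two rules and a reporting requirement:

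1. Summaries of absolute ECG values, the maximum post-dose QTc bands and the counts at 500 msec or more use all Safety Analysis Set patients with at least one on-treatment ECG.
2. Change-from-baseline summaries additionally require a baseline ECG. Shift tables keep the baseline classification but carry a missing-baseline row, so that patients without one remain visible.
3. Report the number of patients without a baseline ECG, and state that the baseline abnormality table is not restricted to patients who have one, so that its not-done category can be filled.

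This needs no new data and only a few lines of text. The one drawback is that absolute and change-from-baseline tables may have different denominators, which printing n in each table makes plain. If every dosed patient has a baseline ECG, the denominators coincide and the results do not change.

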#### **7.2.8. Immunogenicity**

Anti-PF-06647263 antibody data will be collected at baseline and post randomization according to the protocol.

#### **7.3. PK Endpoints**

Blood samples for PK analysis of PF-06647263 (ADC), total antibody, and unconjugated payload will be taken according to the Schedule of Activities given in the protocol.

- **Pharmacokinetic parameters of PF-06647263 (ADC) and total antibody:**

Cycle 1 -  $C_{max}$ ,  $T_{max}$ ,  $AUC_{last}$ ,  $AUC_{inf}$ ,  $AUC_{\tau}$ ,  $t_{1/2}$ , CL, and  $V_{ss}$  as data permit.

Cycle 4 -  $C_{max}$ ,  $T_{max}$ ,  $AUC_{last}$ ,  $AUC_{\tau}$ ,  $t_{1/2}$ , and  $R_{ac}$  as data permit.

- **Pharmacokinetic parameters of Payload (unconjugated payload):**

Cycle 1 -  $C_{max}$ ,  $T_{max}$ ,  $AUC_{last}$ ,  $AUC_{inf}$ ,  $AUC_{\tau}$ , and  $t_{1/2}$  as data permit.

Cycle 4 -  $C_{max}$ ,  $T_{max}$ ,  $AUC_{last}$ ,  $AUC_{\tau}$ ,  $t_{1/2}$ , and  $R_{ac}$  as data permit.

PK parameters will be derived from the concentration-time data as [follows](#):

Parameter	Definition	Method of Determination
AUC last	Area under the concentration-time profile from time zero to the time of the last quantifiable concentration	Linear/Log trapezoidal method
AUC τ	Area under the concentration-time profile from time zero to the time $\tau$ , the dosing interval	Linear/Log trapezoidal method
AUC inf	Area under the concentration-time profile from time zero extrapolated to infinite time	$AUC_{(0-t[last])} + (Clast^*/kel)$ , where Clast* is the predicted serum concentration at the last quantifiable time point estimated from the log-linear regression analysis.
C max	Maximum observed concentration	Observed directly from data
T max	Time for C max	Observed directly from data as time of first occurrence
T ½	Terminal elimination half-life	Log(2)/kel, where kel is the terminal phase rate constant calculated by a linear regression of the log-linear concentration-time curve. Only those data points judged to describe the terminal log-linear decline will be used in the regression.
CL	Clearance	Dose/ AUC inf for cycle 1; Dose/ AUC τ for cycle 4
V ss	Volume of distribution at steady state	CL×MRT
R ac	Observed accumulation ratio	AUC cycle 4, τ / AUC cycle 1, τ

CCI

## 7.5. Covariates

Not applicable.

## 8. HANDLING OF MISSING VALUES

### 8.1. Missing Dates

In compliance with Pfizer standards, if the day of the month is missing for any date used in a calculation, the 1st of the month will be used to replace the missing date unless the calculation results in a negative time duration (eg, date of onset cannot be prior to day one date). In this case, the date resulting in 0 time duration will be used. Pfizer standards are also used if both month and day are missing (Jan 1 unless negative time duration). This excludes the pharmacokinetic, ECG, and pharmacodynamic analyses, which will only use the actual date collected or if date not available deem the data missing.

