# 7. ENDPOINTS AND COVARIATES

## 7.1. Efficacy Endpoint(s)

Objective tumor response, as assessed using the Response Evaluation Criteria in Solid Tumor (RECIST) version 1.1 by calculating the Overall Response Rate (ORR), Progression Free Survival (PFS), and Overall Survival (OS).

All efficacy endpoints are secondary in this study, which include objective tumor response, progression-free survival (PFS), and overall survival (OS) for each tumor type in the expansion cohorts. The above efficacy endpoints are derived based on the disease response per investigator evaluation on the CRF pages, which is the primary method of documentation of disease.

- **Overall Response (OR)** – or Response Rate (RR) is defined as complete response (CR) or partial response (PR) according to RECIST 1.1 ([Appendix 2](#)). Overall response is the best response recorded from first dose until disease progression/recurrence.
- **Progression Free Survival (PFS)** - is defined as the time from Cycle 1 Day 1 (C1D1) to first documentation of disease progression or to death due to any cause, whichever occurs first. Subjects last known to be 1) alive 2) on treatment or within the post-treatment follow-up period and 3) progression-free, are censored at the date of the last disease assessment that verified lack of disease progression. Subjects who start new anti-cancer treatment prior to the end of post-treatment follow-up period and have adequate baseline and on-treatment objective disease assessments without evidence of progressive disease are censored at the date of the last objective disease assessment. Subjects with inadequate baseline or no on-study disease assessments are censored at C1D1 unless death occurred prior to the first planned assessment (in which case the death is an event). Subjects with at least one on-study disease assessment who discontinue treatment without disease progression and without death within 28 days of discontinuation are censored at the date of the last objective disease assessment that verified lack of disease progression (if progression or death is within 28 days of discontinuation the progression or death is an event). Subjects with documentation of progression or death after an unacceptably long interval (>16 weeks) since the previous disease assessment will be censored at the time of the previous assessment.

PFS (days) = [progression/death date – C1D1 + 1].

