- **Overall survival (OS)** is defined as the time from initial dose until death from any cause, and is measured in the intent-to-treat population.

More details of censoring are provided in [Appendix 3](#).

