### 8.2. Efficacy Analysis

Censoring rules for time-to-event endpoints are detailed in [Section 11.3 Appendix 3](#).

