### 11.3. APPENDIX 3: CENSORING DETAILS

**Table 3: Progression Free Survival and Duration of Response**

Situation	Date of Progression/Censoring 	Outcome
Inadequate baseline assessment	Start date (C1D1)	Censored
No on-study assessments	Start date (C1D1)	Censored
Alive, on treatment  and no Progression	Date of last objective tumor assessment	Censored
Progression Documented on or between scheduled tumor assessments prior to treatment discontinuation 	Date of first objective tumor assessment showing objective progression	Progressed (Event)
Treatment discontinuation for undocumented progression	Date of last objective tumor assessment prior to discontinuation 	Censored
Treatment discontinuation due to toxicity or other reason	Date of last objective tumor assessment prior to discontinuation 	Censored
Death prior to first planned tumor assessment	Date of death	Death (Event)
Death without objective progression prior to treatment discontinuation 	Date of death	Death (Event)
Death or progression after 2 or more missed tumor assessments	Date of last objective tumor assessment prior to the event	Censored

1: For date of censorship, if a tumor assessment takes place over a number of days (eg, superficial lesions one day, scans another), the last date is used as the assessment date.

2: or within 28 days of discontinuation of treatment.

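### The partial-date rule in SAP 8.1 has no last-known-alive floor, so an incomplete death date can be imputed to before a date on which the patient was recorded alive

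*SAP*

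**What the plan says.** SAP Section 8.1 gives one imputation rule for the whole study.

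- **Scope.** It applies "if the day of the month is missing for any date used in a calculation". Only the pharmacokinetic, ECG and pharmacodynamic analyses are exempt.
- **Day missing.** The 1st of the month is used. If that makes the duration negative, the rule says: "In this case, the date resulting in 0 time duration will be used".
- **Day and month missing.** "Pfizer standards are also used if both month and day are missing (Jan 1 unless negative time duration").

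Three uses of a death date fall under this rule.

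- **OS** (Section 7.1) "is defined as the time from initial dose until death from any cause".
- **PFS** (Section 7.1) counts death as an event, with conditions. One is "if progression or death is within 28 days of discontinuation the progression or death is an event", and footnote 2 of Appendix 3 Table 3 repeats it ("or within 28 days of discontinuation of treatment"). Section 7.1 also censors a death more than 16 weeks after the previous assessment, and counts a death before the first planned assessment as an event even when there was no on-study assessment.
- **Treatment-emergent events** (Section 7.2.6) include "All deaths from start of treatment until 28 days after the final dose".

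Section 8.2 says only "Censoring rules for time-to-event endpoints are detailed in" Appendix 3. The tables there cover PFS with duration of response, and time to progression. Neither mentions incomplete dates or a date last known alive.

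**The concern.** The 1st of the month and 1 January are the earliest dates compatible with a partial record. The only lower bound is the date that gives zero duration, which for OS is the first dose. That bound suits the rule's own example, an onset date that must not precede day one. For a death it ignores something equally certain: the patient cannot have died before a visit, dose, scan or contact at which he or she was alive.

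Following the rule can therefore produce a death date that the trial's own records contradict. The same date feeds OS, PFS and the classification of deaths as treatment-emergent, so one incomplete date can distort all three.

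**Working it through.** The SAP gives no figure on this point, so there is none to reproduce. The rule is applied as written:

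imputed death = max(1st of month or 1 January, first-dose date).

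The first-dose date is taken as complete.

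**1. Example (assumed dates).** First dose 10 March 2015, last known alive 15 September, true death 24 September; true OS 198 days.
- Day missing: death dated 1 September, OS 175 days, 14 days before the record of life.
- Day and month missing: 1 January precedes first dose, so death is dated 10 March, OS 0 days, 189 days before the record of life.
- With a floor at 15 September: OS 189 days in both cases.

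**2. Day missing.** Let s = day of month − 1, over the 365 days of a non-leap year.
- Mean shift = (7 × 465 + 4 × 435 + 378) / 365 = 5373 / 365 = 14.7 days; maximum 30. This ignores the first-dose bound. On a grid of start dates and deaths 0 to 719 days later with that bound, the mean is 14.5 days and OS never lengthens.
- Last record of life k days before death (assumed): the imputed date precedes it when s > k. k = 7: 269/365 = 74%. k = 14: 185/365 = 51%. k = 21: 101/365 = 28%.
- With last contact instead spread evenly over 0–28, 0–56 or 0–84 days before death, and exponential OS with median 6 to 12 months, the share is 17% to 49%.

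**3. Year only.** Assume exponential survival and a uniform start day. The share set to the first-dose date is 1 − (1 − e^(−a))/a, with a = 365 × ln 2 / median in days.

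| Median (months) | a | Set to first dose | Mean shift, simulated (days) | Same, floor 28 days before death |
|---|---|---|---|---|
| 4 | 2.08 | 58% | 101 | 24.8 |
| 8 | 1.04 | 38% | 132 | 25.8 |
| 12 | 0.69 | 28% | 146 | 26.2 |

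**4. Treatment-emergent window.** A true death g days after the last dose moves to day 28 or earlier when g − s ≤ 28.
- g = 35: 281/365 = 77%. g = 42: 197/365 = 54%. g = 49: 113/365 = 31%. g = 56: 29/365 = 8%. From g = 59: none.
- Example (non-leap year): last dose 10 February, contact 18 March, true death 20 March (day 38), recorded only as March. As written, death is dated 1 March, day 19, 17 days before the contact. With the floor it is 18 March, day 36, outside the window.

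**5. PFS, censored to event.** There are three routes for a patient without earlier progression or other censoring.
- *28-day discontinuation window.* With the day missing, this needs a true death 29 to 58 days after discontinuation (58 = 28 + 30). The percentages in step 4 do not carry over, because the SAP does not say how discontinuation is dated. If it were dated 21 days after the last dose (assumed), deaths at 35, 42 and 49 days after that dose fall on days 14, 21 and 28 after discontinuation and are events already.
- *16-week limit (112 days).* Patient on treatment, last assessment 1 January, true death 30 April of a non-leap year: day 119, censored. Imputed to 1 April: day 90, an event.
- *First planned assessment.* A patient with no on-study assessment is censored at C1D1, but becomes an event if the imputed death falls before that assessment.

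**6. Median OS, n = 15, all deaths observed, exponential survival with median 4 to 12 months.** One day-missing death lowers the sample median by about 1 day and one year-only death by about 7 to 10 days. The sampling SD of the median is 46 to 138 days.

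**7. Effect of a floor, day missing.** The shift becomes min(s, k), with mean 6.1, 10.5 or 13.4 days for k = 7, 14 or 21, against 14.7. For g = 35, 42, 49 the share moved inside the treatment-emergent window is 77%, 0, 0 for k = 7; 77%, 54%, 0 for k = 14; and 77%, 54%, 31% for k = 21, the last unchanged.

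**The case against.** The strongest case against the point is that it has little consequence. The SAP has no hypotheses and no formal tests (Sections 4.1 and 9.1), OS and PFS are secondary and descriptive, and one incomplete date hardly moves a 15-patient median. Earlier deaths and more treatment-emergent deaths are also the cautious direction in a single-arm study. The percentages apply only to deaths whose date is already incomplete, and they depend on assumed contact spacing and survival. Year-only deaths give the largest shifts, yet are the least plausible near treatment, since Section 2.1 plans a follow-up visit within 4 weeks of the last dose. Finally, Section 8.1 invokes company standards and the SAP supplements a protocol. Neither is at hand, and either may treat death dates separately.

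Most of this stands and sets the weight: the percentages are not expected frequencies, and the finding concerns the SAP text alone. It does not remove the error. The SAP states the rule itself, and a date that contradicts the study's own records is not a cautious estimate.

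A reader might go further and infer that the one-way shift in OS is what a last-known-alive floor would cure. It would not: with the floor, the imputed death is still never later than the true one. A reader might also infer that PFS can change only through the 28-day window, or by the treatment-emergent percentages. Section 7.1 gives two further routes, and those percentages are counted from the last dose, not from discontinuation.

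**Conclusion.** The point holds, as a minor one. As written, Section 8.1 can date a death before a record of the patient alive, and it gives zero OS for any year-only death in the calendar year of first dose.

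The day-missing shift (14.7 days on average, maximum 30) follows from the calendar alone. The 74%, 51% and 28% rest on an assumed last record exactly 7, 14 or 21 days before death. The year-only shift of about 101 to 146 days rests on assumed exponential survival with median 4 to 12 months. Misclassification of treatment-emergent deaths, and a PFS change by any of the three routes, are possible, but their frequency cannot be stated.

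The number of incomplete death dates is unknown and probably small. The documents do not support a claim that the OS or PFS medians are materially biased.

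**What to change.** Add to Section 8.1:

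*An incomplete death date is set to the later of the date given by the rule above and the date last known alive (latest recorded contact, visit, dose or assessment). If the date last known alive falls after the recorded month or year of death, the conflict is queried before analysis. The same imputed date is used for OS, PFS and treatment-emergent deaths.*

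This removes every death dated before a record of life and most of the year-only shift. Some earlier-only shift remains, and a patient not recorded alive after day 28 can still be counted inside the treatment-emergent window. Progression dates need no change.

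The cost is a last-known-alive date derived for the few affected patients and a small departure from the company default. The listings in Section 9.2.2.1 already carry the death date, the last tumor assessment date and the most recent progression-free date. They do not name a last-contact date, so that has to be defined and derived.
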